8.1.1.7 TRIAL COMPLIANCE (MEDICATION/DIET/ACTIVITY/OTHER)

Interruptions from the protocol specified treatment for > 12 weeks between

pembrolizumab doses due to toxicity require consultation between the principal and treating investigators and written documentation of the collaborative decision on subject management.

Administration of trial medication will be witnessed by the investigator and/or trial staff. The total volume of trial treatment infused will be compared to the total volume prepared to determine compliance with each dose administered. The instructions for preparing and administering pembrolizumab will be provided in the Pharmacy Manual.

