A DLT is defined as the development of grade 3 or 4 acute GVHD (defined by the Gluckensberg scale), graft rejection, the development of any unexpected grade > 2 toxicity felt to be related to pembrolizumab, or the development of > grade 2 dysfunction of a vital organ felt to be secondary to an immune-related adverse event within 90 days following the initiation of pembrolizumab treatment. For immune-related adverse events that do not meet criteria for a DLT, but do meet criteria for a treatment-limiting toxicity (TLT), for example grade 2 acute GVHD, pembrolizumab will be held until the toxicity has

decreased to \leq grade 1. It will be permanently discontinued if delayed for >12 weeks. For patients who develop GVHD or an immune-related adverse event while on pembrolizumab, corticosteroid therapy and potentially other immunomodulatory agents will be initiated.

If the safety and feasibility of pembrolizumab is confirmed in this patient cohort, a phase II expansion cohort may be considered, particularly for disease subtypes where objective responses have been observed.

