2.2 TRIAL OVERVIEW

The trial overview is depicted in **Table 1**.

Table 1. Trial overview

Initial treatment	Pembrolizumab 200 mg IV on day 1 of each 21 day cycle
Treatment-limiting toxicity (TLT) (for example, grade 2 acute GVHD)	Hold treatment for up to 12 weeks.. For immune-related adverse events that do not meet criteria for a DLT, but do meet criteria for a treatment-limiting toxicity (TLT), for example grade 2 acute GVHD, pembrolizumab can be restarted provided that the toxicity has decreased to $<$ grade 2. For patients who develop GVHD or an immune-related adverse event while on pembrolizumab, corticosteroid therapy and potentially other immunomodulatory agents will be initiated. Re-start treatment with pembrolizumab 200 mg IV on day 1 of each 21 day cycle, provided that the TLT has resolved to \leq grade 1. Permanently discontinue if no improvement in toxicity to \leq grade 1 in 12 weeks.
Dose-limiting toxicity (DLT)	Discontinue treatment. Remove patient from study

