6.2.1.2 DOSE MODIFICATION

Pembrolizumab will be withheld for drug-related, grade 4 hematologic toxicities and drug-related \geq grade 2 or 3 toxicities including laboratory abnormalities, as outlined in **Tables 4 and 5**. Attribution of events to drug will be per investigator/physician discretion.

Table 4. Dose modification guidelines for hematological drug-related adverse events

Toxicity	Grade	Hold Treatment (Y/N)	Timing for restarting treatment	Discontinue Subject (after consultation with the Principal Investigator)
Hematological Toxicity	1, 2, 3	No	N/A	N/A
	4	Yes	Toxicity resolves to Grade 0-1 or baseline	Toxicity does not resolve within 12 weeks of last infusion Permanent discontinuation should be considered for any life-threatening event

Table 5. Dose modification guidelines for non-hematological drug-related adverse events

Toxicity	Hold Treatment For Grade	Timing for Restarting Treatment	Discontinue Subject
Acute GVHD (as defined by the Gluckenberg scale - see appendix)	2 ¹	Toxicity resolves to grade 0-1. Re-start pembrolizumab at 200 mg IV q21 days.	Toxicity does not resolved within 12 weeks of last dose or inability to reduce corticosteroid to 10 mg or less of prednisone equivalent per day within 12 weeks.
	3-4 ¹	Permanently discontinue	Permanently discontinue

Toxicity	Hold Treatment For Grade	Timing for Restarting Treatment	Discontinue Subject
Diarrhea/Colitis	2 ¹	Toxicity resolves to Grade 0-1. Re-start pembrolizumab at 200 mg IV q21 days.	Toxicity does not resolve within 12 weeks of last dose or inability to reduce corticosteroid to 10 mg or less of prednisone or equivalent per day within 12 weeks.
	3-4 ¹	Permanently discontinue	Permanently discontinue
Hypophysitis	2-3 ¹	Toxicity resolves to Grade 0-1.	Toxicity does not resolve within 12 weeks of last dose or inability to reduce corticosteroid to 10 mg or less of prednisone or equivalent per day within 12 weeks.
	4 ¹	Toxicity resolves to Grade 0-1	Toxicity does not resolve within 12 weeks of last dose or inability to reduce corticosteroid to 10 mg or less of prednisone or equivalent per day within 12 weeks.
AST, ALT, or Increased Bilirubin	2 ¹	Toxicity resolves to Grade 0-1. Re-start pembrolizumab at 200 mg IV q21 days.	Toxicity does not resolve within 12 weeks of last dose.
	3-4 ¹	Permanently discontinue (see exception below) ²	Permanently discontinue

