
Note: Permanently discontinue for any severe or Grade 3 drug-related AE that recurs or any life-threatening event.
 
¹ Administer corticosteroid (See also Events of Clinical Interest Guidance Document and Section 8.2.3.2 Events of Clinical Interest).
 
² For patients with liver metastasis who begin treatment with Grade 2 AST or ALT, if AST or ALT increases by greater than or equal to 50% relative to baseline and lasts for at least 1 week then patients should be discontinued.
 
³ Patients with intolerable or persistent Grade 2 drug-related AE may hold study medication at physician discretion. Permanently discontinue study drug for persistent Grade 2 adverse reactions for which treatment with study drug has been held, that do not recover to Grade 0-1 within 12 weeks of the last dose.
 
* Attribution of events to drug will be per investigator/physician discretion; in case of DLT grade toxicity that is deemed to be unrelated to drug, patient can continue on trial with appropriate treatment
			

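### After a toxicity hold of more than 12 weeks, Section 2.1 requires permanent discontinuation while Section 8.1.1.7 asks only for consultation, and the 12 weeks are counted from different starting points

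*Combined protocol and SAP*

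**What the plan says.** Five places in the protocol bear on a long toxicity hold.

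- **Section 2.1**, for immune-related events that meet the treatment-limiting (TLT) but not the dose-limiting (DLT) criteria, with grade 2 acute GVHD as the example: the drug is held until the toxicity is grade 1 or lower, and "It will be permanently discontinued if delayed for >12 weeks".
- **Section 2.2, Table 1**, for TLTs: "Hold treatment for up to 12 weeks", then "Permanently discontinue if no improvement in toxicity to" grade 1 or lower in 12 weeks.
- **Section 6.2.1.2**: Table 4 (hematological) lists as a ground for discontinuation "Toxicity does not resolve within 12 weeks of last infusion". Table 5 (non-hematological) has "Toxicity does not resolve within 12 weeks of last dose", in most rows with a second test on reducing corticosteroids within 12 weeks. Footnote 3 of Table 5 requires permanent discontinuation for persistent grade 2 reactions "that do not recover to Grade 0-1 within 12 weeks of the last dose".
- **Section 6.8** makes stopping treatment mandatory for unacceptable adverse events as described in Tables 5 and 6.
- **Section 8.1.1.7**: "Interruptions from the protocol specified treatment for > 12 weeks between" pembrolizumab doses, where toxicity is the cause, "require consultation between the principal and treating investigators and written documentation of the collaborative decision on subject management".

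No clause says which of these takes precedence.

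**The concern.** Section 2.1 gives a long toxicity delay a fixed outcome, and Section 8.1.1.7 gives it a discretionary one. Where the two overlap, an investigator can follow the protocol and stop the patient for good, or follow the protocol and bring the patient to a discussion that may end in another dose. The overlap includes grade 2 acute GVHD, the protocol's own example of a TLT.

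The different clock starts add a second ambiguity: on a given day the same patient may have passed the limit in one section and not in another.

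Long holds are foreseeable here. For grade 2 enterocolitis, including that caused by acute GVHD, Section 6.6.1 withholds the drug, gives corticosteroids until improvement to grade 1 or lower, and then tapers them over more than a month. What is at stake is consistent handling of re-exposure after immune toxicity, in a trial whose primary objective is tolerability.

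**Working it through.** The plan gives no figure to reproduce. The check sets the rules side by side and converts their clocks using the 21-day cycle (Section 6.2.1.1).

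**Trigger, anchor and consequence**

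| Place | Trigger | 12 weeks counted from | Consequence |
|---|---|---|---|
| 2.1 | length of delay | not stated; read as the delay | permanent discontinuation |
| Table 1 | length of hold; no improvement | not stated; read as the hold | permanent discontinuation |
| Table 4 | non-resolution | last infusion | discontinuation, after consultation |
| Table 5, footnote 3 | non-resolution (steroid test in most Table 5 rows) | last dose; steroid test has no stated start | discontinuation |
| 8.1.1.7 | interval between doses | dose to dose | consultation and documented decision |

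**Converting the clocks**

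- 12 weeks from the last dose = 84 days. The next dose was due at day 21, so the delay past the scheduled dose is 84 − 21 = 63 days = 9 weeks.
- A 12-week delay counted from the scheduled dose = 84 + 21 = 105 days = 15 weeks from the last dose.
- Largest difference: 15 − 12 = 3 weeks. If the hold is counted from toxicity onset within the cycle, the difference lies between 0 and 3 weeks.

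**Running cases through the rules** (Section 2.1 counted from the scheduled dose; Table 5 steroid test assumed met)

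1. Toxicity resolves at week 11 from the last dose; the next dose would fall at week 13. Table 5 is satisfied, the delay is 13 − 3 = 10 weeks, and Section 8.1.1.7 asks for consultation. There is no conflict.
2. Toxicity resolves at week 13 and a dose is considered then. Table 5 calls for discontinuation because the toxicity did not resolve within 12 weeks of the last dose. Section 2.1 does not, because the delay is 10 weeks. Section 8.1.1.7 asks for consultation. The anchors give different outcomes.
3. Toxicity resolves at week 11 but the next dose is considered at week 16. Table 5 does not require stopping. Section 2.1 does, because the delay is 16 − 3 = 13 weeks. Section 8.1.1.7 asks only for consultation. This is the direct clash.
4. Toxicity is still unresolved between weeks 12 and 15. Table 5 says discontinue and Section 2.1 says keep holding. The status differs, but neither permits a dose.

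Beyond 15 weeks from the last dose, Section 2.1 requires discontinuation on any of these readings of its clock, while Section 8.1.1.7 still states only consultation.

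**Reach into the DLT endpoint**

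The DLT definition in Section 2.1 has a window of 90 days from the start of treatment. A disputed restart needs more than 84 days since the last dose. After dose 1 that leaves about 90 − 84 = 6 days of the window. After dose 2 (day 22) it falls at about day 22 + 84 = 106, outside the window.

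**The case against.** The strongest defence is that most of these rules answer different questions. Tables 4 and 5, footnote 3 and the last sentence of Table 1 ask whether the toxicity has settled in time; Section 8.1.1.7 asks how long the gap between doses has been. It can then be read as an added check on late restarts in patients whose toxicity has already resolved. Section 6.8 keeps discontinuation for Table 5 events mandatory. Section 8.1.1.7 never says that treatment may resume, and the Table 4 column heading shows that consultation can accompany discontinuation. Routing each case through the principal investigator also limits divergence.

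Much of this stands. Against Tables 4 and 5, Section 8.1.1.7 can often be reconciled, as the first case shows. It does not dispose of Section 2.1, whose trigger is also the length of the delay and whose outcome is fixed. The mandatory wording in Section 6.8 reaches Table 5 events, which turn on resolution or steroid reduction and not on the dosing interval. The Table 4 heading covers hematological toxicity only. That a restart is open under Section 8.1.1.7 is an inference, but a fair one: an interval between doses presupposes a later dose, and Section 6.2.2 uses very similar consultation wording for interruptions that it expressly allows.

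Three stronger readings are tempting and are not supported.

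- A reader might infer that every held patient faces a 3-week period of opposite instructions. Patients who restart before about week 12 never reach it, 3 weeks is a maximum that depends on an unstated start, and no dose is permitted while toxicity is unresolved under either Section 2.1 or Table 5.
- A reader might infer that the conflict undermines the DLT endpoint. The 90-day window leaves it little room. Section 9.2.4.1 does judge DLT-free status at the end of treatment, but that mismatch in the DLT window is a separate matter.
- A reader might take this for a flaw in the trial's stopping rules. Those are in Sections 9.1.1 and 9.1.3; this is a rule for individual patients.

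**Conclusion.** The inconsistency is real and narrow. For TLT-grade immune-related events that are not DLTs, Section 2.1 requires permanent discontinuation after a delay of more than 12 weeks, while Section 8.1.1.7 states only consultation for more than 12 weeks between doses. The anchors differ by up to 3 weeks. This matters only for holds that reach about 12 weeks, and the difference in anchor matters chiefly for patients whose toxicity resolves between 12 and 15 weeks from the last dose.

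The conclusion rests on reading the clock in Section 2.1 and Table 1 as running over the delay or hold, since neither states a start, and on the 21-day cycle. It is limited to the overlap in scope: the Section 2.1 sentence covers non-DLT immune-related TLTs, and Section 8.1.1.7 covers any toxicity. No sample size, error rate or decision threshold changes, and the effect on 90-day DLT counts is small. The case for correction is patient safety and uniform conduct on re-exposure.

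**What to change.** Reconcile Sections 2.1, 2.2 (Table 1), 6.2.1.2 (Tables 4 and 5 with footnote 3), 6.8 and 8.1.1.7 to one rule. The amended text should state:

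- the event that starts the 12 weeks, in the same words everywhere, including the steroid-reduction test in Table 5;
- whether the trigger is the length of the interruption, non-resolution of the toxicity, or both;
- whether consultation under Section 8.1.1.7 can lead to a further dose or only documents the decision to stop.

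Which rule and which start apply is a clinical decision for the sponsor, and this review takes no position on it. The cost is a wording amendment; the design, the sample size and the analysis are unaffected.

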8.1.2 CLINICAL PROCEDURES/ASSESSMENTS

8.1.2.1 ADVERSE EVENT (AE) MONITORING

The investigator or qualified designee will assess each subject to evaluate for potential new or worsening AEs as specified in the trial flow chart, and more frequently if clinically indicated. Adverse events will be graded and recorded throughout the study and during the follow-up period according to NCI CTCAE Version 4.0. All AEs of unknown etiology associated with pembrolizumab exposure should be evaluated to determine if they are possibly events of clinical interest (ECI) of a potentially immunologic etiology (irAE). See Section 6.6.1.1 and the separate guidance document in the administrative binder regarding the identification, evaluation, and management of AEs of a potential immunological etiology. Please refer to Section 8.2 for detailed information regarding the assessment and recording of AEs.

8.1.2.2 PHYSICAL EXAMINATION

The investigator or qualified designee will perform a complete physical examination during the screening period. Clinically significant abnormal findings should be recorded as medical history. A complete physical examination should be performed during screening and repeated as per the frequency defined in the Study Flow Chart. After the first dose of trial treatment, new clinically significant abnormal findings should be recorded as AEs.

8.1.2.3 VITAL SIGNS

The investigator or qualified designee will take vital signs at screening, prior to the administration of each dose of trial treatment and at treatment discontinuation as specified in the trial flow chart (Section 7.0). Vital signs should include temperature, pulse, respiratory rate, weight and blood pressure. Height will be measured at screening only.

8.1.2.4 ELECTROCARDIOGRAM

A standard 12-lead ECG will be performed using local standard procedures at screening. Clinically significant abnormal findings should be recorded as medical history.

8.1.2.5 EASTERN COOPERATIVE ONCOLOGY GROUP (ECOG) PERFORMANCE STATUS

The investigator or qualified designee will assess ECOG status (Appendix) at screening, prior to the administration of each dose of pembrolizumab, and at discontinuation of trial treatment as specified in the trial flow chart.

8.1.2.6 ASSESSMENT OF DISEASE

8.1.2.6.1 CRITERIA FOR ASSESSMENT OF DISEASE

The efficacy of pembrolizumab will be evaluated using the following disease-specific criteria

- **B cell lymphomas** - The International Working Group response criteria will be utilized as the primary means to assess disease response to pembrolizumab in B cell lymphoma patients ³⁹, and is the basis for all protocol guidelines related to disease status.
- **MDS** - The International Working Group response criteria in myelodysplasia will be utilized as the primary means to assess disease response to pembrolizumab in MDS patients ⁴⁰, and is the basis for all protocol guidelines related to disease status.
- **AML** - The European LeukemiaNet guidelines will be utilized as the primary means to assess disease response to pembrolizumab in AML patients ⁴¹, and is the basis for all protocol guidelines related to disease status.

8.1.2.6.2 B CELL LYMPHOMA SUBJECT DISEASE RESPONSE ASSESSMENT

Response in B cell lymphoma patients using bone marrow analysis (where applicable), as well as PET/CT (aggressive B cell lymphomas and Hodgkin lymphoma) or CT (low-grade B cell lymphomas) is based on the International Working Group criteria ³⁹. Local reading (investigator assessment with site radiology reading) will be used to determine subject eligibility and for subject management. No central radiology review will be performed. Assessment of lymphoma-related B symptoms should occur with each disease response assessment.

8.1.2.6.3 DISEASE ASSESSMENT OF IMMUNOTHERAPEUTIC AGENTS

Note - this section pertains to subjects with B cell lymphomas only. Immunotherapeutic agents such as pembrolizumab may produce anti-tumor effects by potentiating endogenous cancer-specific immune responses, which may be functionally anergic. The response patterns seen with such an approach may extend beyond the typical time course of responses seen with cytotoxic agents, and can manifest a clinical response after an initial increase in tumor burden or even the appearance of new lesions.

Standard response assessment criteria may not provide a complete response assessment of immunotherapeutic agents such as pembrolizumab. Therefore in the setting where a subject assessment shows PD, study drug may be continued until next disease response assessment provided that the subjects' clinical condition is stable. Repeat scans after suspected "pseudoprogression" should be obtained in 4-6 weeks; if scans confirm progression, pembrolizumab will be discontinued. If progression is not confirmed on repeat imaging, the patient may continue on therapy. However, imaging should occur at any time where there is clinical suspicion of progression.

Note - with the next disease response assessment if the disease is clinically stable or clinically improved, an exception may be considered to continue treatment upon consultation with the principal investigator.

8.1.2.6.4 AML SUBJECT DISEASE RESPONSE ASSESSMENT

Response in AML patients using peripheral blood and bone marrow analysis is based on the European LeukemiaNet guidelines ⁴¹. Local review by a site hematopathologist will be used to determine subject eligibility and management. No central pathology review will be performed.

8.1.2.6.5 MDS SUBJECT DISEASE RESPONSE ASSESSMENT

Response in MDS patients using peripheral blood and bone marrow analysis is based on the International Working Group response criteria in myelodysplasia ⁴⁰. Local review by a site hematopathologist will be used to determine subject eligibility and management. No central pathology review will be performed.

8.1.2.6.6 TIMING OF DISEASE ASSESSMENTS

Uniform disease response assessments in all subjects will occur every 12 weeks following the first disease response assessment at week 12 (see **Table 8**).

Table 8. Disease response assessments

Indication	Assessment Frequency
B cell lymphoma, AML and MDS	Every 12 weeks following first assessment at week 13 up to 12 months. Subsequent disease response assessments are at the discretion of the treating physician.

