Briefly, patients will undergo baseline eligibility screening within 2 weeks prior to enrollment, including a medical history, physical examination, and assessment of performance status and hematology and chemistry parameters. Baseline assessment of disease status will be based on results of a bone marrow aspirate and biopsy for patients with AML and MDS, and a CT/PET scan (with a bone marrow exam for history of disease involvement) for patients with lymphoma. Baseline and subsequent bone marrow and peripheral blood samples will be obtained for correlative assays. Disease response assessment (bone marrow aspirate and biopsy and/or CT/PET) will be performed at baseline, and then every 3 months for 2 years, as well as any time if relapse is suspected. Specific procedures to be performed during the trial, as well as their prescribed times and associated visit windows, are outlined in the trial flow chart – Section 7.0. Details of each procedure are provided in Section 8.0 – trial procedures. After 24 months, ongoing disease re-assessments will be performed at the discretion of the treating physician. Any patient who experiences biopsy-proven disease progression at any time will be removed from study, and alternative treatment can be recommended at the treating physician's discretion. Subjects are not eligible for re-treatment on with pembrolizumab in the setting of this protocol should they experience a disease relapse after completing 24 months of therapy. After the end of treatment, each subject will be followed for 30 days for adverse event monitoring (serious adverse events will be collected for 90 days after the end of treatment). Subjects who discontinue treatment for reasons other than disease progression will have post-treatment follow-up for disease status until disease progression, initiating a non-study cancer treatment, withdrawal of consent, or becoming lost to follow-up. All subjects will be followed by telephone contact for overall survival until death, withdrawal of consent or the end of the study, whichever comes first.

The primary objective of this trial is to determine whether administration of pembrolizumab is tolerable in patients who have experienced disease relapse following alloSCT. Secondary objectives include analysis of efficacy parameters (ORR, DOR, OS). Correlative studies to examine the effect of PD-1 blockade therapy on T cell parameters and clonality, as well as on donor chimerism are planned as exploratory analyses.

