8.1.2.6.8 DISEASE ASSESSMENT DURING THE TRIAL

Disease assessments should be performed as outlined in Table 8. There is a +/- 7 day window for assessments performed after Day 1. For MDS and AML patients, bone marrow biopsy will be the method of assessing disease response (along with peripheral blood counts). For subjects with lymphoma, PET and diagnostic CT scans will be performed for aggressive B cell lymphoma and Hodgkin lymphoma subjects, while CT scans alone will be performed for subjects with low-grade lymphomas. Disease assessments and imaging should continue to be performed on protocol for 2 years after initiation of pembrolizumab treatment, and then until documented disease progression, the start of new anti-cancer treatment, withdrawal of consent, death, or the end of the study, whichever occurs first.

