8.1.5.2 TREATMENT PERIOD

Visit requirements are outlined in Section 7.0 – trial flow chart. Specific procedure-related details are provided above in Section 8.1 – trial Procedures. Each on-study visit will be scheduled based on the date of the week 0 (day 1) visit. Required visits are outlined below. The treatment period commences on the day of the first dose of pembrolizumab, and ends following a 21 day cycle. During the study treatment period, subjects will be regularly monitored to assess the safety and anti-tumor activity of the treatment.

Baseline/Week 0

Subjects who meet all of the inclusion criteria and none of the exclusion criteria will return to the clinic within 28 days after screening for baseline assessments.

The following baseline assessments will be completed prior to the first dose of pembrolizumab:

- Physical examination and vital signs, including ECOG performance status
- Laboratory assessments and blood sampling:
- Chemistry

- TSH, T3, FT4
- Hematology: CBC and differential
- Urine pregnancy test, if applicable
- Correlative studies
- Confirmation of Medical History
- Assessment of AEs
- Recording of concomitant medications

Weeks 1, 2, 3

Clinic/laboratory visits will occur every week through the Week 4 visit. The following procedures will be completed at each visit, unless otherwise specified:

- Physical examination and vital signs, including ECOG performance status
- Laboratory assessments and blood sampling:
 - Chemistry
 - Hematology: CBC and differential
 - Assessment of AEs
 - Recording of concomitant medications

Weeks 4, 7, 10, 13, 16, 19, 22, 25, 28, 31, 34, 37, 40, 43, 46, 49, 52, 55, 58, 61, 64, 67, 70, 73, 76, 79, 82, 85, 88, 91, 94, 97, 100, 103

Subjects continuing on study past Week 4 will have visits every 3 weeks through Week 49, and then at physician discretion. The following procedures will be completed at each visit, unless otherwise specified:

- Physical examination and vital signs, including ECOG performance status
- Laboratory assessments and blood sampling:
 - Chemistry
 - TSH, T3, FT4 (every 6 weeks)
 - Hematology: CBC and differential

- Assessment of adverse events
- Recording of concomitant medications

Weeks 13, 25, 37, 49, 61, 73, 85, 97 - Disease assessments

- Bone marrow aspirate and biopsy for all patients with AML and MDS and B cell lymphoma patients with bone marrow involvement
- Correlative studies
- Radiology assessment (CT or CT/PET) for B cell lymphoma patients only

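### Table 8 makes disease assessment optional after 12 months while the rest of the protocol fixes it every 12 weeks to 2 years, so late duration of response may depend on when someone chooses to look

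*Combined protocol and SAP*

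**What the plan says.** The current text gives two schedules.

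**Shorter rule.**
- Table 8 in section 8.1.2.6.6 gives "Every 12 weeks following first assessment at week 13 up to 12 months", followed by "Subsequent disease response assessments are at the discretion of the treating physician".
- Section 8.1.2.6.8 directs sites to that table: "Disease assessments should be performed as outlined in Table 8".
- Section 8.1.5.2 describes visits as "every 3 weeks through Week 49, and then at physician discretion", directly under a list of visits that runs to week 103.

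**Longer rule.**
- Section 2.1 says response assessment "will be performed at baseline, and then every 3 months for 2 years, as well as any time if relapse is suspected", and places discretion a year later: "After 24 months, ongoing disease re-assessments will be performed at the discretion of the treating physician".
- The flow chart (7.4 and 7.5) marks imaging and marrow at weeks 61, 73, 85 and 97.
- Section 8.1.5.2 lists eight disease-assessment weeks, the last being week 97.
- Section 8.1.2.6.9 keeps patients with stable disease or a response on the 12-weekly flow-chart schedule, with no 12-month limit.
- The last sentence of 8.1.2.6.8 says "Disease assessments and imaging should continue to be performed on protocol for 2 years after initiation of pembrolizumab treatment", then extends assessment to progression or another stopping event.

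Section 8.1.6.4 sets 12-weekly disease follow-up for patients who stop treatment for a reason other than progression.

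DOR runs from response to progression or relapse (3.2) and is summarized by Kaplan-Meier (Table 12; 9.2.4.2.2). Neither place says how to handle a missed or irregular assessment.

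**The concern.** A site cannot follow both schedules. The shorter one is not an isolated slip: it has an echo in 8.1.5.2, and Table 8 is the table that 8.1.2.6.8 tells sites to use.

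Progression is known only when somebody looks. With a common fixed interval, the dating error is bounded and similar for everyone. If looking is optional in year 2, silent progression is recorded when a physician happens to order a scan or marrow, or not at all. Both errors lengthen the recorded DOR.

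Ascertainment would also differ by treatment status. A patient who stopped treatment in remission would be assessed every 12 weeks under 8.1.6.4, while one still receiving drug in month 15 would be assessed at discretion under Table 8.

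**Working it through.** **1. Reproduce the schedule.** Starting at week 13 and adding 12 weeks up to week 104 gives weeks 13, 25, 37, 49, 61, 73, 85 and 97. That is eight assessments, matching 8.1.5.2 and the flow chart.

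**2. Apply Table 8.** Cutting at 12 months (about week 52) leaves weeks 13, 25, 37 and 49. Week 49 is 49/4.345 = 11.3 months. So 8 − 4 = 4 assessments become optional.

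**3. Extra dating delay.** The gap to the next look after week 49 is not in the documents, so 24 and 48 weeks are assumptions. For progression just after week 49:
- on schedule it is found at week 61, a lag of at most 12 weeks;
- next look at week 73: 73 − 61 = 12 weeks later than on schedule;
- next look at week 97: 97 − 61 = 36 weeks later than on schedule.

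With a single look at week 97, the extra delay falls to 24 weeks for progression in weeks 61–73, 12 weeks for weeks 73–85, and none for weeks 85–97.

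**4. Effect on DOR (illustration only).** Assumptions not in the documents: response first seen at week 13, exponential DOR with true median m weeks, no assessment triggered by symptoms, and no other censoring. Week 49 is then 36 weeks after response, and week 97 is 84 weeks after.
- Share of responders progressing between weeks 49 and 97 = 0.5^(36/m) − 0.5^(84/m).
- Observed median = time from response to the first look at or after m.
- Observed proportion still in response at 65 weeks = 0.5^(t/m), where t is the last look at or before 65 weeks: t = 60 with 12-weekly looks, t = 36 with a single look at week 97.

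| True median m (weeks) | Progress in weeks 49–97 | Median, 12-weekly | Median, 24-weekly after week 49 | Median, one look at week 97 | Median, no look after week 49 | In response at 65 weeks, 12-weekly | In response at 65 weeks, one look at week 97 |
|---|---|---|---|---|---|---|---|
| 26 | 28% | 36 | 36 | 36 | 36 | 0.202 | 0.383 |
| 39 | 30% | 48 | 60 | 84 | not reached | 0.344 | 0.527 |
| 52 | 29% | 60 | 60 | 84 | not reached | 0.449 | 0.619 |
| 78 | 25% | 84 | 84 | 84 | not reached | 0.587 | 0.726 |

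With one late look, the 65-week proportion is about 14 to 18 percentage points above the 12-weekly value. The median moves only in some rows. With 24-week gaps only the 39-week row moves, and the 65-week proportion does not change, because the week-73 look falls 60 weeks after response.

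**The case against.** The textual conflict is hard to dispute; its consequences can be.

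- **Suspected relapse is still assessed.** Section 2.1 requires it at any time, and 8.1.2.6.3 and 8.1.2.6.9 require imaging on clinical suspicion in lymphoma. The flow chart keeps blood counts and examination at each dosing visit. This stands: the bias is confined to progression that gives no clinical sign, and the table above, which ignores triggered looks, overstates it.
- **Only some patients are exposed.** Patients off treatment without progression stay on 12-weekly follow-up (8.1.6.4). This stands: the four lost assessments concern patients still on treatment after 12 months.
- **Sites may follow the flow chart.** Several sections direct them there, and no bias arises if they do. True, but 8.1.2.6.8 directs them to Table 8.
- **Little depends on DOR.** It is secondary and descriptive, drawn from responders among at most 26 patients, and no decision rule uses it. This stands.

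Two stronger readings are tempting and are not supported. From the week-49 sentence a reader might infer that 18 dosing visits lose their safety checks: weeks 52 to 103, (103 − 52)/3 + 1 = 18. But the flow chart marks adverse-event review and laboratory tests at each of them. Vital signs (8.1.2.3), performance status (8.1.2.5), laboratory review (8.1.3.1) and assessment for events of clinical interest (8.2.3.2) are also required before each dose. A patient who is dosed is checked.

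A reader might also infer damage to the primary outcome, since 9.2.4.1 refers to DLT-free status at the end of treatment. Section 2.1 attaches a 90-day window to the DLT definition. How far that window reaches is a separate question, and an optional response assessment in year 2 does not bear on it.

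**Conclusion.** The contradiction is real and sits in the current text. Followed literally, Table 8 makes four of eight scheduled disease assessments optional for patients on treatment beyond 12 months, and gives them looser ascertainment than patients who have stopped. The direction of the effect is clear: silent year-2 progression is dated late or missed, and the Kaplan-Meier tail for DOR is biased upward.

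The size is not fixed by the documents. It rests on the assumed gap between looks, the assumed DOR, and how much progression is silent. Under the assumed gaps the extra delay is at most 12 to 36 weeks. If true DOR is short (median 26 weeks in the illustration) the observed median does not move and only the tail does. This is worth correcting, but it does not threaten the trial's main conclusion.

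**What to change.** 1. Change Table 8 to every 12 weeks from week 13 through week 97, in line with 2.1, the flow chart and 8.1.2.6.8. Remove the discretion sentence from the table.
2. Reconcile the week-49 visit sentence in 8.1.5.2 with its own visit list and with the flow chart.
3. Reconcile the period after 24 months. Section 2.1 makes assessment discretionary then, while 8.1.2.6.8 and 8.1.6.4 continue it until progression or another stopping event. Simply moving the discretion sentence to month 24 would leave this conflict in place.
4. It would help to state in 9.2.4.2.2 how DOR is dated and censored when a scheduled assessment is missed.

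Relative to the flow chart, items 1 and 2 cost wording only. A site now working from Table 8 would perform up to four more assessments per patient, all of them already in the flow chart.
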